#### 8.2.3.3 DETERMINING WHICH ACTIGRAPH MONITORING APPROACH TO USE

The decision to use either of the above options will be based on several factors. There are several potential barriers to participant compliance with keeping the actigraph monitor in their possession (Section 8.2.3.1), including higher probability of device damage due to longer term use (e.g. wrist band breaks, charger fails, etc.), and higher probability that the device will go into Halt mode due to complete loss of battery life. If a device goes into Halt mode, the activity monitor would need to be physically collected back from the participant and the data downloaded, with a new device initialized and provided back to the participant. If we find that an individual study participant is struggling to comply with this approach, we may recommend shifting to the serial mailing approach (Section 8.2.3.2) for a given participant. We will continuously monitor compliance with both approaches and may need to shift our strategy to favor the approach that yields the higher compliance with the study procedures.

#### 8.2.4 SELF-REPORTED PHYSICAL ACTIVITY DATA

For participants who agree to complete surveys electronically, a Redcap electronic survey will be emailed to participants 7 days after each scheduled Actigraph assessments to collect the number of minutes of moderate or brisk physical activity completed during the preceding week. If a participant reports doing no activity during the preceding week, then zero (0) minutes will be recorded. If participants do not respond to the email survey, the research coordinator will contact the participant by phone to collect this information. There is a potential that a participant who has not been compliant with the scheduled wear period will be asked to self-report PA in a week that they were not also wearing the actigraph device, which will limit our ability to correlate self-report to objectively measured PA in all instances; however, we suspect that averaged on the 12 month period of the trial, self-reported PA in a close window of time relative to the actigraph wear period will correlate with objectively measured PA within an approximate window of time.

### 8.2.5 ADMINISTRATION OF QUESTIONNAIRES

Several questionnaires will be administered in this study at the baseline and follow-up assessment (see Section 11). For on-site visits, participant responses will be entered into an electronic data capture form. For home-visits, a paper form will be used to record responses and transcribed into the electronic data system after the visit by the research coordinator. All participants will be offered the ability to complete questionnaires for the follow-up assessments via an electronic survey (RedCap). Incomplete responses will be follow-up by phone or collected at the study visits.

### 8.2.6 DPP SESSION ATTENDANCE AND CONTENT TRACKING

Upon referral to a participating DPP, the research coordinator will create a record in a RedCap database linking the study participant to a specific DPP. This will serve as the mechanism of communicating a referral to the local DPP. Local DPP program coordinators will be asked to report attendance and outcome measures as outlined in Section 11.13. The local DPP programs will be asked to provide data they are already collecting from their participants as required by the CDC. Complete and validated data entry will be used to determine compensation to local DPPs as described in Section 5.6.2.2. Local DPPs will **not** have access to the JHU research databases.

## 8.3 SAFETY AND OTHER ASSESSMENTS

Since this study is focused on lifestyle modification (physical activity, healthy nutrition, and weight management) for diabetes prevention, it is considered to be a low-risk study with no obvious safety concerns. Participants will be informed of their laboratory results, height, and weight measurements at the study visit.

Participants' individual electronic medical records will be reviewed during screening and assessment of adverse events. Health Insurance Portability and Accountability Act (HIPAA) rules, other relevant federal or state laws, and local institutional requirements should be followed, as applicable.

A brief AE evaluation will be conducted (Section 11.20) at the 6 month and 12 month study visits.

## 8.4 ADVERSE EVENTS AND SERIOUS ADVERSE EVENTS

### 8.4.1 DEFINITION OF ADVERSE EVENTS (AE)

An AE is defined as any untoward medical occurrence, unintended disease or injury or any untoward clinical signs (including an abnormal laboratory finding) in subjects or other persons whether or not related to the investigational medical device.

- This includes events related to the investigational device.
- This includes events related to the procedures involved (any procedure in the clinical investigation plan).
- For users or other persons this is restricted to events related to the investigational device, i.e., HCPs.

The study team will record all of the adverse events documented in CRF. During the study all adverse events that occurred should be recorded in the CRF tables. Only clinically significant abnormal lab test results as determined by researchers will be reported as adverse event.

#### 8.4.2 DEFINITION OF SERIOUS ADVERSE EVENTS (SAE)

An Adverse Event that led to death; significant deterioration in health, that either resulted in life-threatening illness or injury, permanent impairment of a body function or permanent damage to a body structure, or required in-patient hospitalization or prolongation of existing hospitalization, or resulted in medical or surgical intervention to prevent any one of the outcomes listed above.

- This includes device deficiencies that might have led to a serious adverse event if a) suitable action had not been taken, or b) intervention had not been made, or c) if circumstances had been less fortunate.
- A planned hospitalization for a pre-existing condition, or a procedure required by the clinical investigation plan, without a serious deterioration in health, is not considered to be a serious adverse event.

A serious adverse event may be an unanticipated adverse device effect. An unanticipated adverse device effect means any serious adverse effect on health or safety or any life-threatening problem or death caused by, or associated with, a device, if that effect, problem, or death was not previously identified in nature, severity, or degree of incidence in the investigational plan or application (including a supplementary plan or application), or any other unanticipated serious problem associated with a device that relates to the rights, safety, or welfare of subjects.

##### 8.4.3.2 RELATIONSHIP TO STUDY INTERVENTION

For all collected AE's, the clinician who examines and evaluates the subject will determine the AE's causality based on temporal relationship and his/her clinical judgment. The degree of certainty about causality will be graded using the categories below.

- Definitely related - There is clear evidence to suggest a causal relationship, and other possible contributing factors can be ruled out. The clinical event, including an abnormal laboratory test result, occurs in a plausible time relationship to study intervention and cannot be explained by concurrent disease or other drugs or chemicals. The response to withdrawal of the intervention (dechallenge) should be clinically plausible.
- Probably related - There is evidence to suggest a causal relationship, and the influence of other factors is unlikely. The clinical event, including an abnormal laboratory test result, occurs within a reasonable time after administration of the study intervention, is unlikely to be attributed to concurrent disease or other drugs or chemicals, and follows a clinically reasonable response on withdrawal (dechallenge). Rechallenge information is not required to fulfill this definition.
- Possibly related - There is some evidence to suggest a causal relationship (e.g. the event occurred within a reasonable time after administration of the study intervention). However, other factors may have contributed to the event (e.g. the subject's

clinical condition, other concomitant events). Although an AE may rate only as “possibly related” soon after discovery, it can be flagged as requiring more information and later be upgraded to “probably related” or “definitely related,” as appropriate.

- Not Related - The AE is completely independent of the study intervention, and/or evidence exists that the event is definitely related to another etiology. There must be an alternative, definitive etiology documented by the clinician.

#### 8.4.3.3 EXPECTEDNESS

Based on the experience from our pilot study, we do not anticipate any intervention-related AEs. Although the study intervention aims to increase PA, the emphasis is on increase in leisure time PA (i.e. walking) or light-moderate PA rather than moderate or strenuous exercise. Thus, exercise-related AEs, such as cardiovascular events, would be considered unexpected (unanticipated) in this study. On the other hand, muscle soreness, fatigue, or musculoskeletal injuries that relate directly to PA, would be considered expected (anticipated) AEs. Any participant who reports shortness of breath or chest pain during periods of PA will be required to undergo additional medical clearance before continuing in the study. The PI, [name] MHS, will be responsible for determining whether an AE is anticipated or unanticipated. An AE will be considered unanticipated if the nature, severity, or frequency of the event is not consistent with the risk information previously described for mHealth-based interventions targeting weight loss or physical activity.

#### 8.4.4 TIME PERIOD AND FREQUENCY FOR EVENT ASSESSMENT AND FOLLOW-UP

The occurrence of an AE or SAE may come to the attention of study personnel during study visits and interviews of a study subject presenting for medical care, or upon review by a study monitor. All AEs including local and systemic reactions not meeting the criteria for SAEs will be captured on the appropriate CRF. Information to be collected includes event description, time of onset, clinician’s assessment of severity, relationship to study intervention (assessed by clinician), and time of resolution/stabilization of the event. All AEs occurring while on study must be documented appropriately regardless of relationship. All AEs will be followed to adequate resolution.

Any medical condition that is present at the time the subject is screened will be considered as baseline and not reported as an AE. However, if the study subject’s condition deteriorates at any time during the study, it will be recorded as an AE. UPs will be recorded in the data collection system throughout the study.

Changes in the severity of an AE will be documented to allow an assessment of the duration of the event at each level of severity to be performed. AEs characterized as intermittent require documentation of onset and duration of each episode.

The PI will record all reportable events with start dates occurring at any time after informed consent is obtained until 7 (for non-serious AEs) or 30 days (for SAEs) after the last day of study participation. At each study visit, the RC will inquire about the occurrence of AEs/SAEs since the last visit. Events will be followed for outcome information until resolution or stabilization.

#### 8.4.5 ADVERSE EVENT REPORTING

AEs will likely be reported first to research coordinators during scheduled study visits or during follow-up communications and will be documented in the participant’s electronic case report form.

Research Coordinators are expected to enter adverse event information immediately into REDCap. The Research Coordinator will report the date of onset and resolution of the AE, description of the problem, adverse event preferred term using the MedDRA medical terminology, and the perceived grade of the AE. The Research Coordinator will contact the PI and Project Manager immediately by phone or text message for any perceived Grade 4 or higher AE (life-threatening consequences; urgent intervention indicated, or death related to adverse event). For all AEs entered into REDCap, the PI and project manager will immediately receive an email notification indicating that an adverse event has been reported, prompting further AE assessment. The PI will review the event and determine the grade, relatedness, and adverse event preferred term using the MedDRA medical terminology. If the lead PI ([name]) is not available, the research coordinator will contact the co-investigator ([name]) who will serve as a back-up.

The PI will record all reportable events with start dates occurring at any time after informed consent is obtained until 7 days (Grades 1-2) or 30 days (Grades 3-5) after the last day of study participation. At each study visit, the research coordinator will inquire about the occurrence of AEs since the last visit. Events will be followed for outcome information until resolution or stabilization.

The PI will inform the IRB, DSMB, and NIH program officer immediately when five grade 3 AEs are determined to be “probably related” to the study intervention. The DSMB will convene an ad hoc meeting by teleconference or in writing as soon as possible.

The DSMB will provide recommendations to the study team and sponsor (NIH). If the NIH determines that an unanticipated intervention effect presents an unreasonable risk to subjects, investigations, or parts of investigations presenting that risk will be terminated as soon as possible.

#### 8.4.7 REPORTING OF PREGNANCY

Women who are pregnant at the time of screening or who are planning pregnancy during the study period will be excluded from participation in the study. Since pregnancy can result in spurious changes in A1C and would be expected to result in weight increases and possible higher BG due to insulin resistance, pregnancy during the study would be considered a protocol violation. Women who report becoming pregnant during the study will be withdrawn from the study.

### 8.5 UNANTICIPATED PROBLEMS

#### 8.5.1 DEFINITION OF UNANTICIPATED PROBLEMS (UP)

The Office for Human Research Protections (OHRP) considers unanticipated problems involving risks to participants or others to include, in general, any incident, experience, or outcome that meets all of the following criteria:

- Unexpected in terms of nature, severity, or frequency given (a) the research procedures that are described in the protocol-related documents, such as the Institutional Review Board (IRB)-approved research protocol and informed consent document; and (b) the characteristics of the participant population being studied;
- Related or possibly related to participation in the research ("possibly related" means there is a reasonable possibility that the incident, experience, or outcome may have been caused by the procedures involved in the research); and
- Suggests that the research places participants or others at a greater risk of harm (including physical, psychological, economic, or social harm) than was previously known or recognized.

#### 8.5.2 UNANTICIPATED PROBLEM REPORTING

The investigator will report unanticipated problems (UPs) to the reviewing Institutional Review Board (IRB) and to the Data Coordinating Center (DCC)/lead principal investigator (PI). The UP report will include the following information:

- Protocol identifying information: protocol title and number, PI's name, and the IRB project number;
- A detailed description of the event, incident, experience, or outcome;
- An explanation of the basis for determining that the event, incident, experience, or outcome represents an UP;
- A description of any changes to the protocol or other corrective actions that have been taken or are proposed in response to the UP.

To satisfy the requirement for prompt reporting, UPs will be reported according to the Johns Hopkins University School of Medicine's Organizational policy on prompt reporting of reportable events.

### 9 STATISTICAL CONSIDERATIONS

## 9.1 STATISTICAL HYPOTHESES

This non-inferiority trial is designed to demonstrate that the Sweetch fully automated dDPP is no worse than the standard of care hDPP with respect to participant attainment of the CDC's benchmark for type 2 diabetes risk reduction. We will assume a percentage of "success" (i.e. attainment of the binary composite endpoint) in both the dDPP and hDPP of 50% and an equivalence limit,  $d$ , of 15%.

The percentage of participants that meet the primary endpoint will be compared between the two randomized groups. The null hypothesis is that the percentage for those in the standard treatment hDPP ( $\pi_s$ ) is better than the percentage on the experimental fully automated treatment dDPP ( $\pi_e$ ) by 15 or more percentage points, versus the alternative that the percentage for those on the new treatment is  $\pi_s - 15$  or better, i.e.

$$H_0: \pi_s \geq \pi_e + 15$$

$$H_a: \pi_s - 15 < \pi_e$$

In selecting the equivalence margin for this non-inferiority trial, we considered the guidance provided by the U.S. FDA. As we seek to evaluate a composite endpoint that has not previously been evaluated in a RCT, our assumptions are based mainly on the primary endpoint of the 5% weight loss outcome at 12 months (one of the three endpoints in our composite endpoint). Weight loss has been shown to be the most significant driver of type 2 diabetes risk reduction. In the landmark DPP trial, the risk difference in attainment of 5% weight loss at 12 months among participants randomized to the intensive lifestyle intervention (active control in the present trial) vs. placebo was 46.7% (95% CI 43.1% - 50.2%). Thus, the fraction of our equivalence margin to the entire effect of the active control is ~32%, which is significantly less than the recommended 50% threshold suggested by the FDA.

Considering the low rates of referral and retention in the hDPP, a 15% difference in the primary endpoint would be considered acceptable in our clinical judgment in order to gain the advantages of a cheaper and scalable alternative to the current available intervention. In addition, there is significant variability in outcomes attained in real-world DPPs to justify this equivalence margin. Among a subset of hDPPs participating in our study (N=5), the proportion of completers achieving the 5% weight loss outcome was 50% (range 47% to 60%) and the 4% weight loss and 150 minutes of PA outcome was 50% (range 29% to 80%) (unpublished data). Of note, however, the outcomes reported by hDPP are calculated based on program completers (per protocol analysis). In our trial, we plan on conducting an intent-to-treat analysis. Thus, we expect that the observed  $\pi_s$  will be closer to the 30-40% range based on participant-level data across the U.S. from the CDC's national DPP.

## 9.2 SAMPLE SIZE DETERMINATION

Under a 1:1 randomization design, with a significance level (alpha) of 5% and 80% power, and assuming 50% of the participants achieve the primary outcome in both arms, 138 participants are required to enroll in each of the two arms, for a total study sample size of  $n = 276$ . Assuming a conservative attrition rate of 25% at 12 months, the adjusted sample size is set to 184 per group (368 total) to ensure the minimal necessary analyzable sample of 276 is retained. If there is truly no difference between the hDPP and dDPP, then 276 participants are required to be 80% sure that the upper limit of a one-sided 95% confidence interval will exclude a difference in favor of the hDPP of more than 15%. While it was previously noted that  $\pi_s$  will be closer to the 30-40% range, we used 50% in the non-inferiority sample size calculations as this choice yields the largest necessary sample size among all choices for  $\pi_s$ , and thus makes the study robust, in terms of statistical power, to other values for  $\pi_s$ .

## 9.3 POPULATIONS FOR ANALYSES

Consistent with the **intention-to-treat (ITT)** principle, results of all study participants will be evaluated according to initial randomization regardless of whether they adhered to their assigned treatment and regardless of protocol violations or deviations. Analyses of effectiveness endpoints, however, will exclude participants who withdraw from the study or withdraw consent. Effectiveness analyses will be performed for the ITT population. All primary statistical analyses of effectiveness measures will be unadjusted and two-sided tests of significance will be used. A per-protocol analysis will also be conducted using the population of program completers in each group, as defined in Section 3.3, to benchmark outcomes against CDC standards.

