### 7.3 LOST TO FOLLOW-UP

A participant will be considered lost to follow-up if he or she fails to return for the 12 month study visit and is unable to be contacted by the study site staff.

The following actions must be taken if a participant fails to return to the clinic for a required study visit:

- The site will attempt to contact the participant and reschedule the missed visit within 30 days and counsel the participant on the importance of maintaining the assigned visit schedule and ascertain if the participant wishes to and/or should continue in the study.
- Before a participant is deemed lost to follow-up, the investigator or designee will make every effort to regain contact with the participant (where possible, 3 telephone calls and, if necessary, a certified letter to the participant's last known mailing address or local equivalent methods). These contact attempts should be documented in the participant's study record.
- Should the participant continue to be unreachable, he or she will be considered to have withdrawn from the study with a primary reason of lost to follow-up.

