#### 9.4.2 MISSING OUTCOMES DATA

We anticipate that there will be a very low amount of missing data for the outcomes of A1C and weight for study completers, since both measures are collected by the technician at the study visits. However, since the outcome of PA measurement relies on participants to wear the ActiGraph devices at 1-month intervals, there may be more missing data for this outcome variable. If more than 5% of data for this outcome variable is missing, the primary analysis will be based on multiple imputation. A sensitivity analysis will also be done using a complete case analysis (i.e. participants with 100% of PA data) and if results differ significantly, the primary analysis will be interpreted in light of results from the sensitivity analysis.

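### Section 9.3 calls the effectiveness analyses ITT but drops participants who withdraw or are lost, and no planned effectiveness analysis keeps everyone randomised

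*Combined protocol and SAP*

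**What the plan says.** Section 9.3 of the combined protocol and SAP opens with the intention-to-treat principle: participants are evaluated as randomised, "regardless of whether they adhered to their assigned treatment and regardless of protocol violations or deviations". The next sentence narrows this: "Analyses of effectiveness endpoints, however, will exclude participants who withdraw from the study or withdraw consent". The section then names the ITT population for those same analyses. The only other effectiveness set is narrower still: "A per-protocol analysis will also be conducted using the population of program completers in each group".

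Section 7.3 says of a participant who stays unreachable that "he or she will be considered to have withdrawn from the study with a primary reason of lost to follow-up".

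Section 9.2 plans on the same footing: "Assuming a conservative attrition rate of 25% at 12 months, the adjusted sample size is set to 184 per group", the purpose being "to ensure the minimal necessary analyzable sample of 276 is retained".

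On missing outcomes, section 9.4.2 offers an expectation for weight and A1C, limited to people who complete the study: "We anticipate that there will be a very low amount of missing data for the outcomes of A1C and weight for study completers". It then turns to ActiGraph data and sets a trigger: "If more than 5% of data for this outcome variable is missing, the primary analysis will be based on multiple imputation". The complete-case sensitivity analysis is likewise defined on activity data. Section 9.4.8 repeats both rules. The endpoint definition in section 3.2 codes 0 when no component is achieved and does not address unknown status.

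**The concern.** Read together, sections 9.3 and 7.3 remove ordinary loss to follow-up from the primary comparison while the report would still call it ITT. Randomisation does not protect a comparison restricted to people who stayed, because staying may depend on the arm and on how the participant is doing. The trial is open-label, and the arms differ in kind: an app kit sent by mail, or scheduled sessions with a coach. Equal attrition therefore cannot be taken for granted.

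The imputation rule does not help. Under section 3.2, activity data change the endpoint only for someone with at least 4% but less than 5% weight loss and no A1C success. Weight and A1C decide nearly every case, and their absence has either a rule of exclusion or no rule at all. At stake is whether a non-inferiority claim describes everyone assigned to the app or only those who remained.

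**Working it through.** **1. The plan's own sample size.** Inputs from section 9.2: 50% success in both arms, margin 15 points, one-sided 5%, power 80%, attrition 25%.

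n per arm = 2 × 0.5 × 0.5 × (1.645 + 0.842)² / 0.15² = 137.4, rounded up to 138, so 276 in total. Then 138 / 0.75 = 184 per arm, 368 in total. Both figures reproduce; the arithmetic is not the defect.

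**2. Who leaves.** 368 × 0.25 = 92, and 368 − 92 = 276. This is a planning figure, not a ceiling.

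**3. What handling each group has.**

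| Participant | Handling in the plan |
|---|---|
| Stops the programme, stays in the study | Kept (7.1, 9.3) |
| Withdraws, or is lost and unreachable | Excluded (9.3 with 7.3); no sensitivity analysis |
| Reachable, not withdrawn, no 12-month weight or A1C | No rule |
| Withdrawn by the study team (for example for pregnancy, 8.4.7) | Unclear: 7.2 separates those who withdraw from those who are withdrawn, and 9.3 mentions only the former |
| Activity data missing | Imputed if more than 5% is missing; complete-case sensitivity analysis (9.4.2, 9.4.8) |

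**4. Illustration of size.** The documents give no attrition by arm and no success rate among dropouts, so both are assumptions here. Let p be success among all randomised, r retention, and k the success rate in dropouts divided by that in retained participants.

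- Success rate in the retained set: s = p / (r + (1 − r)k), with n = 184r per arm.
- P(declare non-inferiority) = Φ((0.15 − (s_h − s_d)) / SE − 1.645), with SE unpooled.

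Example: hDPP 40%, dDPP 25% (a true 15-point deficit), attrition 15% in hDPP and 35% in dDPP, k = 0. Then s_h = 0.40/0.85 = 0.471, s_d = 0.25/0.65 = 0.385 and SE = 0.0598. (0.15 − 0.086)/0.0598 − 1.645 = −0.574, giving 28%.

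False non-inferiority at hDPP success of 30/35/40%, true deficit 15 points, nominal 5%:

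| Attrition hDPP / dDPP | Dropouts never succeed (k = 0) | Half the retained rate (k = 0.5) |
|---|---|---|
| 25% / 25% | 0.5 / 0.6 / 0.6% | 2.0 / 2.1 / 2.2% |
| 20% / 30% | 3.3 / 4.7 / 6.4% | 3.8 / 4.4 / 4.9% |
| 15% / 35% | 13 / 20 / 28% | 7 / 8 / 10% |

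If dropouts succeed at their own arm's retained rate (k = 1), the figure is 5% in every row.

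Section 9.2 uses a one-sided 95% interval, but section 9.3 speaks of two-sided tests. With a two-sided 95% interval (1.96 in place of 1.645, nominal error 2.5%), the last row becomes 7 / 12 / 19% and 3.5 / 4.4 / 5.4%.

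**5. The opposite direction.** True equality at 37.5%, attrition 30% in hDPP and 20% in dDPP, one-sided 5%: power is 40% (k = 0), 68% (k = 0.5) and 82% (k = 1).

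**6. Missing counted as failure.** All 184 per arm analysed, equal 25% attrition, true 15-point deficit, hDPP success 30-40%: false non-inferiority is 12-13% at k = 0.5 and 21-25% at k = 1, because failures added to both arms shrink the difference. It is not a safe primary rule.

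**The case against.** The strongest reply is that section 9.3 states its exclusion openly, so withdrawn and lost participants do have a rule. That stands. A reader might infer that nothing at all governs missing 12-month weight or A1C; the text does not support that. The gaps are the participants still in the study without a value, and the lack of any sensitivity analysis for those excluded.

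A reader might also infer that the plan is biased towards declaring non-inferiority. The documents do not support this either. Their one attrition figure is 25%, not split by arm and described as conservative, and equal attrition gives no inflation. Inflation needs appreciably higher attrition in the dDPP arm together with poorer success among its dropouts. What hints exist, such as low hDPP retention (9.1) and the greater dDPP engagement hypothesised in 2.2, point the other way, though they concern the programme rather than the study. In that direction the cost is power.

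Retention measures are real: visit payments (5.6.2.1), home visits (5.6.3), repeated contact attempts (5.6.5), rescheduling (7.3), and the effort to keep non-engagers in the study (7.1). They limit attrition but do not change the analysis set.

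Finally, a reader might see a conflict between withdrawal after a joint injection (6.5) and adjustment for steroid use during the study (9.4.5, 9.4.7). There is none: 6.5 also lists oral steroids, and nothing withdraws a participant for those.

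**Conclusion.** The point holds as a defect in the definition of the primary analysis set. Followed as written, the plan yields a retained-participant comparison under an ITT label, leaving out about 92 of 368 at the planned attrition, and no planned effectiveness analysis includes all randomised participants. That conclusion rests on the text alone.

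The size of any bias is not known and its sign is open. It rests on assumed attrition by arm, assumed success among dropouts and the one-sided 5% level. Across the cases shown it runs from none (equal attrition), through little at a 10-point gap (at most 6.4%), to 13-28% or 7-10% at a 20-point gap against the dDPP arm. With attrition higher in the hDPP arm, power falls to 40% or 68%. The set and the handling of missing values need to be fixed before outcome data are seen, the more so because section 6.4 leaves the biostatistician unmasked.

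**What to change.** - **Section 9.3:** define the primary effectiveness set as all randomised participants in their assigned arm, leaving out only data a participant refuses to have used. Keep the present set as a supportive analysis named 'retained participants', so that it is not confused with the programme completers of section 3.3.
- **Section 9.4.2:** multiply impute missing 12-month weight and A1C by arm, using baseline and 6-month weight and A1C, site and engagement. Derive the composite within each imputation, counting the A1C component only where baseline A1C is 5.7-6.4%. State that this assumes data missing at random. It does not by itself remove the not-at-random bias illustrated above.
- **Sensitivity:** add a tipping-point analysis with arm-specific deltas. Missing counted as failure should be one point on that grid, not the primary rule.
- **Unclear cases:** state how the analysis treats participants withdrawn by the study team and reachable participants who miss the 12-month visit.

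The cost is protocol and SAP wording plus programming, with no new data, visits or participants. The downside is a more complex primary analysis that rests on a stated missing-data assumption.

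Separately from this point, the joint-injection withdrawal note in section 6.5 must be reconciled with that section's look-back period for prohibited medications and with the withdrawal conditions in section 7.2. No clinical rule is proposed here.
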